In the recent years, the aim of IBD treatment has evolved from symptomatic control to deep remission, which is defined as the absence of symptoms, markers of inflammatory activity, and endoscopic lesions, and is associated with fewer admissions to hospital, surgeries and better HRQoL. Main current treatment modalities for UC and CD include 5-aminosalicylates, corticosteroids, immunomodulators (including thiopurines, methotrexate, tacrolimus, cyclosporine, and biological therapies), and surgery. Conventional treatment with corticosteroids and immunomodulators has not been able to reduce the complications of the disease or modify its course. Over the last decade, biologic treatments, such as infliximab, adalimumab, certolizumab pegol, golimumab and vedolizumab has been used in patients with moderate to severe CD, and in those with acute severe UC who failed to respond to corticosteroids.

At present, early introduction of immunomodulators and biologic agents in patients with more serious disease is probably the most widely accepted management strategy. Treatment of IBD with anti-TNF $\alpha$  since IBD diagnosis, albeit capable of inducing and maintaining mucosal healing and reducing surgery and hospitalization rates, may imply overtreatment of patients with milder forms of disease, thus emphasizing the need for accurate prognostic markers to guide patient selection. It is worth mentioning that although anti-TNF $\alpha$  therapy is thought to be an effective approach for IBD, up to 30% of patients do not respond to induction therapy (primary non-response) and a significant proportion loses response over time (secondary non-response). Very often patients profile in randomized controlled trials is quite restrictive and not representative of patients routinely treated under usual clinical conditions, especially, in terms of presence co-morbidities, concomitant treatments and previous use of biologics.

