## 6. Methodology

### 6.1. Study design

In order to meet the objectives of the present study, a retrospective, non-interventional, multicentre observational study including 25 gastroenterology sites from all around Spain has been designed. Participating investigators will be gastroenterologists and will include consecutive patients diagnosed with UC or CD that started treatment with biologics between June 2011 and June 2013, after giving written informed consent. The study will consist of one only visit in which investigators will collect patients' sociodemographic (age, gender, race, level of education, smoking habits alcohol intake) and clinical (concomitant diseases, date of diagnosis, previous treatment, current treatment, disease activity when starting treatment with biologics and at the study visit, current situation in terms of treatment with biologics) data from medical charts or directly from patients (in case of discrepancy, the information coming from medical charts will be preferable). Time since patients started biological treatment until study visit or until lack of treatment response or until treatment change will constitute the reference period for the study. In order to fulfill current legislations regarding non-interventional studies, investigators will commit to follow usual clinical practice.

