#### **6.3.2. Inclusion criteria**

- Adult patients (aged  $\geq 18$ )
- Patients diagnosed with UC or CD according to the "World Gastroenterology Organization Practice Guidelines for the Diagnosis and Management of IBD in 2010"
- Patients naive to biologics that started treatment with biologics between June 2011 and June 2013
- Patients in whose biological treatment was prescribed according to daily clinical practice.
- Patients that gave written informed consent

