#### 6.4.5. Main outcome

Non responders will be those patients not achieving a reduction in HBI of at least 2 points from baseline for CD, and a decrease in the PMS of at least 2 points for UC.. In the cases where these indexes are not available, clinical response will be evaluated according to physician criteria at short term (10 weeks after starting the anti-TNF) and at long term (at least 6 months after starting the anti-TNF). Primary non-responders (PNR) were defined as patients with no clinical response at short term. Loss of response (LOR) was defined as loss of the effect of the drug along the follow up in a patient with initial response.

Reasons to stop the drug will be classified as follows: PNR, LOR, side effects (SE), remission and other.

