3.7. Inclusion Criteria

- Adult patients (aged ≥ 18).
- Patients diagnosed with UC or CD according to the "World Gastroenterology Organization Practice Guidelines for the Diagnosis and Management of IBD in 2010".
- Patients naïve to biologics that started treatment with biologics between June 2011 and June 2013.
- Patients in whose biological treatment was prescribed according to daily clinical practice.
- Patients that gave written informed consent.

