4. STUDY POPULATIONS

4.1. Definition of study populations to analyse

Study Population: All patients who meet the selection criteria and have given their informed consent will be included in the analysis.

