6.1. Biological treatment

We will describe the treatments administered to the patients:

- Number and percentage of patients who received each biological treatment (infliximab, adalimumab, golimumab and others).
- Number and percentage of patients who intensified the biological treatment and the reason (increased doses, decreased intervals between doses or both) according to the different biological treatment specified.
- Number and percentage of patients who discontinued the treatment and the reason (PNR, LOR, PR, SE, remission and others) according to the different biological treatment specified.
- Number and percentage of patients who received a second biological treatment and the description of the different biological treatments and the number of biological treatments received after discontinuation.
- Number and percentage of patients who received concomitant treatment with corticosteroids or immunosuppressives during induction phase. Description of the different concomitant treatment received.

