7. EFFICACY ASSESSMENT

7.1. Efficacy Assessment; general considerations

Non responders will be those patients not achieving a reduction in HBI of at least 2 points from baseline for CD and a decrease in the PMS of at least 2 points for UC.

In the cases where these indexes are not available, clinical response will be evaluated according to physician criteria at short term (10 weeks after starting the anti-TNF [*primary response and primary non-response*]) and at long term (at least 6 months after starting the anti-TNF [*primary response maintenance and loss of response*]).

We will calculate the following variables:

- **Lack response during the induction phase (primary non response):** Those patients who 10 weeks after starting the anti-TNF not achieving a reduction in HBI of at least 2 points from baseline for CD and a decrease in the PMS of at least 2 points for UC. In the cases where these indexes are not available, clinical response will be evaluated according to physician criteria at short term (*primary response and primary non-response*).
- **Loss of response during the maintenance phase (secondary loss of response):** Those patients who at least 6 months after starting the anti-TNF not achieving a reduction in HBI of at least 2 points from baseline for CD and a decrease in the PMS of at least 2 points for UC. In the cases where these indexes are not available, clinical response will be evaluated according to physician criteria at short term (*primary response maintenance and loss of response*).

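### Outcomes are timed from the anti-TNF, while entry and baseline are tied to the first biologic, and nothing keeps a later drug's study-visit score out of the loss-of-response outcome

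*SAP*

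**What the plan says.** Entry under Protocol 6.3.2 is for "Patients naive to biologics that started treatment with biologics between June 2011 and June 2013", and SAP 3.7 repeats this. The primary objective (Protocol 5.1, SAP 3.5) concerns response to biological therapy. Protocol 6.1 defines the reference period as "Time since patients started biological treatment until study visit or until lack of treatment response or until treatment change", and Protocol 6.4.4 collects disease activity (HBI for CD, PMS for UC) at the start of that period and at the study visit. SAP 4.1 sets no limit by drug class: "All patients who meet the selection criteria and have given their informed consent will be included in the analysis".

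The outcomes use a different origin. SAP 7.1 defines primary non-response as "Those patients who 10 weeks after starting the anti-TNF not achieving a reduction in HBI of at least 2 points from baseline for CD", with the matching PMS rule for UC. It defines loss of response by the same index rule at least 6 months after the anti-TNF start. The anti-TNF start appears four times in that section. Protocol 6.4.5 has the same origin, "at short term (10 weeks after starting the anti-TNF) and at long term (at least 6 months after starting the anti-TNF", but attaches it to the physician judgement used when the indices are missing.

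Later biologics are foreseen. Protocol 6.4.4 records any new biologic after discontinuation, with dates and reasons. SAP 6.1 counts second biologics. Protocol 7.4 speaks of a different biologic started within the reference period and makes a separate analysis of those patients optional.

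**The concern.** Both outcomes are dependent variables of the primary logistic models. If the drug that starts the outcome clock is not the drug that defines entry and baseline, the outcome may be undefined or may describe the wrong treatment. Neither document equates the two terms, limits entry to anti-TNF starters, or says how a first biologic of another class is scored.

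The second gap does not depend on drug class. A patient may lose response to the first biologic, move to another and do well on it. The only follow-up index listed is the one at the study visit. Judged by that index, the patient can be counted as having maintained response. The reverse can also happen: a patient who did well until stopping for side effects, and then fared badly on a second drug, can be counted as a loss of response. Errors of this kind blur the outcome that the comorbidity odds ratios are meant to explain.

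**Working it through.** **1. The plan's own figure.** Protocol 7.1 takes 10 events per variable, at most 10 variables and 50% non-response. N = (10 × 10) / 0.50 = 200 per disease, as stated. The site target agrees: 25 sites × 8 patients = 200. The 50% is stated for biologics in general, so a common time origin leaves N at 200.

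**2. Time origins side by side.**

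| Element | Tied to | Place |
|---|---|---|
| Entry | first biologic | Protocol 6.3.2, SAP 3.7 |
| Objective | biological therapy | Protocol 5.1, SAP 3.5 |
| Reference period | start of biological treatment | Protocol 6.1 |
| Baseline HBI/PMS | start of reference period | Protocol 6.4.4 |
| Analysis set | all eligible, consented patients | SAP 4.1 |
| Primary non-response | 10 weeks from anti-TNF | SAP 7.1 |
| Loss of response | at least 6 months from anti-TNF | SAP 7.1 |

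The last two rows do not match the others, and no rule links them.

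**3. Cost of the class mismatch, if it occurs.** The documents give no share f of first biologics outside the anti-TNF class. Assume 0% to 20%. Per disease, evaluable = 200(1 − f), events = 0.5 × evaluable, and permitted variables = events / 10, rounded down.

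- f = 0%: 200 evaluable, 100 events, 10 variables
- f = 1%: 198, 99, 9
- f = 5%: 190, 95, 9
- f = 10%: 180, 90, 9
- f = 20%: 160, 80, 8

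At f = 0 nothing is lost.

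**4. Switchers.** Let B be the index at the start of the first biologic and V the index at the study visit. Under SAP 7.1 a patient has lost response if B − V is below 2, and has maintained it otherwise. Protocol 6.4.4 lists no index between B and V, so for a switched patient V is measured on or after a later drug. B − V then spans two drugs, and the course on the first drug does not enter.

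**5. How late V can be.** Starts ended in June 2013. The protocol's reference list includes a consensus paper dated 2016, so this version was written in 2016 or later. Even the latest starters would therefore be seen at least about 30 months after starting (end of June 2013 to the start of 2016). SAP 7.1 sets no upper limit, so such a visit qualifies.

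**6. Which outcome is exposed.** No week-10 index is among the listed variables, so primary non-response will mostly rest on physician judgement. The index problem in step 4 therefore falls on loss of response.

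**The case against.** The strongest reply is that the anti-TNF, definite and singular, most naturally means the drug with which the patient entered. Protocol 6.1 ends the reference period at treatment change, so a second drug starts no new clock and later data lie outside the period. This is probably what was intended. It does not settle the matter: SAP 7.1 never refers to the reference period, Protocol 6.4.4 places the second measurement at the study visit for everyone, and Protocol 7.4 puts a change of biologic inside the period. SAP 7.2 offers discontinuation as a candidate covariate, but a covariate does not correct a miscoded outcome.

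Two further replies stand. First, a reader might infer that some included patients have no valid outcome. The documents do not show this. SAP 6.1 describes "patients who received each biological treatment (infliximab, adalimumab, golimumab and others", but its last category is open. Protocol section 4 says "biologic treatments, such as infliximab, adalimumab, certolizumab pegol, golimumab and vedolizumab has been used", yet does not tie that list to the inclusion window or sort the drugs by class. Certolizumab pegol is on that list and not named in the SAP, so the open category need not mean another class. Second, swapping the term alone would not help switchers, whose visit index is measured after the change whichever start date is used.

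Limiting entry and objective to anti-TNF starters would also remove the class mismatch. Protocol 6.4.5 takes its response definitions from a study of anti-TNF therapy, so applying the same windows to another class is a real choice. A rule for switchers would still be needed.

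**Conclusion.** The point holds in two parts of unequal weight. The time origins differ on the page, so any included patient whose first biologic is not an anti-TNF would have no defined week-10 or month-6 date; how many there are, if any, is unknown. The more important part rests on no assumption about drug class: loss of response is not confined to the first biologic and can be misclassified in patients who switched.

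The size cannot be stated, because neither document gives a switching rate. Protocol section 4 says that an appreciable share of patients lose response over time, without a number. Misclassification unrelated to comorbidity would in general pull the odds ratios towards 1. A reader might infer that the errors gather in patients with comorbidities, through the choice of drug class. Nothing in the documents links class or switching to comorbidity, so no direction of bias can be claimed. Nor does the point show the sample size to be too small: 200 per disease stands.

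**What to change.** - In SAP 7.1 (four places) and Protocol 6.4.5 (two places), replace the anti-TNF with the index biologic, defined as the first biologic started between June 2011 and June 2013. Date baseline, week 10 and month 6 from its start.
- State that both primary outcomes use only assessments made before the index biologic is stopped or changed.
- Classify patients who stopped or switched from the recorded date and reason for discontinuation, together with physician criteria. Set the category for each reason in advance. Protocol 6.4.5 lists primary non-response, loss of response, side effects, remission and other; SAP 6.1 adds partial response, so the lists need to be aligned.
- Report response to later biologics only descriptively, under SAP 6.1.
- Reconcile Protocol 7.4 with Protocol 6.1 on whether a change of biologic falls inside the reference period.

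The cost is a few sentences. Start dates, discontinuation dates and reasons are already collected under Protocol 6.4.4. There is a small downside: some switchers' study-visit indices go unused, and windows taken from an anti-TNF study would apply to any other class. The rule should be settled before database lock, when the SAP is due to be signed, so that the choice is not made with the data in view.

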#### 6.4.4. Study variables

The following **sociodemographic variables** will be collected from patients' medical records or directly from patients during the study visit, straight after their inclusion in the study:

- Age
- Gender
- Race (caucasian, asiatic, latin, black, other)
- Level of education (uneducated, primary education, secondary education, university education)
- Working status (student, self-employed, employed by other, retired, housework, unemployed, temporarily unable to work, permanently unable to work, other)
- Smoking habits (non-smoker, ex-smoker, smoker, number of cigarettes per day)
- Alcohol intake (units per week).

The following **clinical variables** will be collected from patients' medical records (when available) or directly from patients during the study visit, straight after their inclusion in the study:

- Date of diagnosis (UD or CD).
- Disease activity at the beginning of the reference period and at the study visit through collection of the following variables:
  - For UC patients:
    - Partial Mayo Score (PMS) (9 point scale that excludes the endoscopic appearance of the mucosa)
    - General disease activity:
      - Mild: up to four bloody stools daily and no systemic toxicity
      - Moderate: four to six bloody stools daily and minimal toxicity
      - Severe: more than six bloody stools daily and signs of toxicity, such as fever, tachycardia, anaemia, raised erythrocyte sedimentation rate.
      - Fulminant: More than ten bloody stools daily, continuous bleeding, anaemia requiring blood transfusion, abdominal tenderness and colonic dilatation on plain abdominal radiographs.
    - Disease anatomic extent: proctitis, left-sided colitis or pancolitis.
    - Endoscopy findings:

- Normal or inactive disease
- Mild disease (erythema, decreased vascular pattern, mild friability)
- Moderate disease (marked erythema, lack of vascular pattern, friability erosions)
- Severe disease (spontaneous bleeding, ulceration).
- For CD patients:
  - Harvey-Bradshaw Index (HBI) (a simplified version of CDAI)
  - General disease activity:
    - Mild to moderate: ambulatory patients able to tolerate oral alimentation without manifestations of dehydration, toxicity, abdominal tenderness, painful mass, obstruction or >10% weight loss.

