7.2. Primary efficacy endpoint

- **Primary endpoint:** Evaluate the impact of the co-morbidities profile in IBD patients on treatment response to biological therapy.

The analysis that will be performed to answer the objective will be the following:

In order to determine the level of correlation between the co-morbidities profile and treatment response, adjusting for sociodemographic and clinical profile of patients, two logistic regression models will be conducted. The dependent variable of the models will be the **lack of response during the induction phase and the loss of response during the maintenance phase**. In both models independent variables will include all comorbidities, as well as sociodemographic and clinical variables as covariates.

- The following potential variables will be considered for the analysis:
 - Crohn's Disease or Ulcerative Colitis.
 - Myocardial Infarction (yes/no).
 - Congestive Heart Failure (yes/no).
 - Peripheral Vascular Disease (yes/no).
 - Cerebrovascular Disease (yes/no).
 - Dementia (yes/no).
 - Chronic Obstructive Pulmonary Disease (yes/no).
 - Connective Tissue Disease (yes/no).
 - Peptic Ulcer Disease (yes/no).
 - Mild Chronic Hepatopathy (yes/no).
 - Diabetes Mellitus (yes/no).
 - Hemiplegic (yes/no).
 - Moderate-Severe Chronic Kidney Disease (yes/no).
 - Diabetes with lesions in target organs (yes/no).
 - Solid Tumor (yes/no).
 - Leukemia (yes/no).
 - Lymphoma (yes/no).

- Moderate-Severe Chronic Hepatopathy (yes/no).
 - Solid tumor with metastases (yes/no)
 - Acquired immunodeficiency syndrome (AIDS) (yes/no).
 - Gender.
 - Race (caucasian, asiatic, latin, black, other).
 - Level of education (uneducated, primary education, secondary education, university education).
 - Working status (student, self-employed, employed by other, retired, housework, unemployed, temporarily unable to work, permanently unable to work, other).
 - Smoking habits (non-smoker, ex-smoker and smoker).
 - Alcohol abuse (yes/no).
 - Time from diagnostic of disease.
 - Disease location.
 - Discontinuation the biological treatment (yes/no)
- Each one of the variables will be compared between the subjects with primary non-response vs primary response and primary response maintenance vs loss of response and those variables whose p-value is lower than 0.1 are considered potential variables for performing a logistic regression analysis.

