14.3 EFFICACY DATA			
14.3.1 Primary efficacy parameter			
14.3.1.1 Comparison of subjects presenting comorbidities, sociodemographic and clinical variables based on the lack of response during the induction phase (primary response vs primary non-response)	COMP1 / COMP4	Study population	
14.3.1.2 Logistic regression: Lack of response during the induction phase	RL	Study population	
14.3.1.3 Comparison of subjects presenting comorbidities, sociodemographic and clinical variables based on the loss of response during the maintenance phase (primary response maintenance vs loss of response)	COMP1 / COMP4	Study population	
14.3.1.4 Logistic regression: Loss of response during the maintenance phase	RL	Study population	

TITLE	TABLE TYPE	ANALYSIS SET	COMMENT
14.3.2	Secondary efficacy parameters		
14.3.2.1	Logistic regression: Lack of response during the induction phase based on the extraintestinal manifestations	RL	Study population
14.3.2.2	Logistic regression: Loss of response during the maintenance phase based on the extraintestinal manifestations	RL	Study population
14.3.2.3	Comorbidities description according to IBD	CAT2	Study population
14.3.2.4	Comparations of comorbidities between IBD severe vs non-severe at baseline	COMP1	Study population
14.3.2.5	Logistic regression: IBD severe or non-severe at baseline based on the comorbidities and patient disease	RL	Study population

TYPES OF TABLES

Examples for descriptive analysis of categorical variables:

CAT2

		Variable 2						
		Value a		Value b		...		
Variable 1	Value a	N	%	N	%	N	%	Total
	Value b							
	...							
	Total							

Examples for descriptive analysis of continuous variables:

CONT2

			Variable 1			
			N	Mean	Median	Standard deviation
Variable 2	Value a					Minimu
	Value b					m
	...					

Examples for multivariable analysis or comparations:

Chi-square results

COMP1

	Value	df	Asym. Sig. (2-sided)	Exact Sig. (2-sided)	Exact Sig. (1-sided)
Pearson Chi-square					
Continuity correction					
Likelihood Ratio					
Fisher's Exact Test					
Linear by linear association					
N of valid cases					

T-test results

COMP 4

Independent Samples Test

			Variable	
			Equal variances assumed	Equal variances not assumed
Levene's Test for Equality of variances	F			
t-test for Equality of means	t			
	df			
	Sig. (2-tailed)			
	Mean Difference			
	Std. Error Difference			
	95% Confidence Interval of the difference		Lower	Upper

Logistic regression results

LR

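### The SAP's loss-of-response variable drops the initial response that the protocol requires, so the second primary model may mix induction failure with true loss of response

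*SAP*

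**What the plan says.** Protocol 6.4.5 separates two failures. Primary non-response is no clinical response at short term (10 weeks). Loss of response is "loss of the effect of the drug along the follow up in a patient with initial response".

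SAP 7.1 lists the variables it will calculate. Its loss-of-response variable covers "Those patients who at least 6 months after starting the anti-TNF not achieving a reduction in HBI of at least 2 points from baseline", with the corresponding 2-point rule on the partial Mayo score (PMS) for UC. Where the indexes are missing, the same bullet falls back on "physician criteria at short term (*primary response maintenance and loss of response". The paragraph above it assigns those two categories to long term, at least 6 months.

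SAP 7.2 screens candidate variables by comparing "primary response maintenance vs loss of response and those variables whose p-value is lower than 0.1". Both group names presuppose a primary response.

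The only population in SAP 4.1 is: "All patients who meet the selection criteria and have given their informed consent will be included in the analysis". Appendix 1 assigns this Study population to Table 14.3.1.4, "Logistic regression: Loss of response during the maintenance phase", and also to Tables 14.3.1.3 and 14.3.2.2.

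On timing, Protocol 6.1 says that the time from the start of the biologic "until study visit or until lack of treatment response or until treatment change will constitute the reference period for the study". Protocol 6.4.4 collects "Disease activity at the beginning of the reference period and at the study visit".

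**The concern.** The derivation and the group labels describe different variables. The derivation asks only whether the patient is a non-responder at 6 months or later. The labels, and the protocol, ask whether a responder later lost the effect. A programmer could follow either and get different event counts.

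Loss of response is one of the two dependent variables for the primary objective. SAP 7.3 uses it again as the second dependent variable for the extraintestinal-manifestations objective. If primary non-responders enter, the second model partly re-tests the first. A comorbidity that acts only on induction could then appear to predict loss of response. It could also appear protective, if the primary non-responders who carry it respond late and are counted as maintained responders.

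**Working it through.** **1. The plan's own figure.** Protocol 7.1 assumes 10 events per variable, at most 10 variables and 50% non-response: 10 × 10 / 0.50 = 200 per disease, which reproduces. The phase to which the 50% belongs is not stated.

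**2. The two definitions, patient by patient.**

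| Week 10 | 6 months or later | Protocol 6.4.5 | SAP 7.1, read literally |
|---|---|---|---|
| Response | Response | Maintained | Maintained |
| Response | No response | Loss of response | Loss of response |
| No response | No response | Primary non-response only | Loss of response |
| No response | Response | Primary non-response only | Non-event, so grouped with maintained |

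The last two rows differ, and no text in either document removes those patients from the second model.

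**3. Inputs for an illustration.**
- N = 400 (Protocol 7.1).
- Primary non-response 30%, the upper figure in Protocol section 4.
- The 50% read as primary non-response plus later loss (an assumption).
- a = share of primary non-responders with a late non-response value (not given, so varied from 0 to 1).

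Primary non-responders: 0.30 × 400 = 120. Primary responders: 280. True losses: 0.50 × 400 − 120 = 80. Loss rate among responders: l = 80/280 = 0.286.

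**4. Share of coded events that never responded:** 120a / (120a + 80).
- a = 1: 120/200 = 60%
- a = 0.5: 60/140 = 43%
- a = 0.25: 30/110 = 27%
- a = 0: 0%

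Varying primary non-response over 10–30% and loss among responders over 20–40%, the share is 22–68% at a = 1, 12–52% at a = 0.5 and 6–35% at a = 0.25.

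**5. Effect on an odds ratio.** Take a comorbidity with odds ratio 3 (or 2) for primary non-response and 1 for true loss. Assume a primary non-response risk of p0 = 0.28 without it, and the same a and l in both groups. Then p1 = 0.538 for odds ratio 3 and 0.4375 for odds ratio 2. The coded event risk at each p is:
- remaining primary non-responders respond late: a·p + l(1 − p)
- remaining primary non-responders have no late value: [a·p + l(1 − p)] / [a·p + (1 − p)]

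Example, a = 1 and odds ratio 3: the risks are 0.28 + 0.286 × 0.72 = 0.486 and 0.538 + 0.286 × 0.462 = 0.670. The odds are 0.944 and 2.033, and their ratio is 2.15.

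| a | OR 3, rest have no late value | OR 3, rest respond late | OR 2, rest have no late value | OR 2, rest respond late |
|---|---|---|---|---|
| 1 | 2.15 | 2.15 | 1.58 | 1.58 |
| 0.5 | 1.81 | 1.27 | 1.40 | 1.16 |
| 0.25 | 1.51 | 0.95 | 1.25 | 0.97 |
| 0 | 1.00 | 0.59 | 1.00 | 0.74 |

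The correct value in every cell is 1.

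**6. Variables supported at 10 events each.** Under the protocol's definition there are 80 events pooled, so 8 variables, or 40 per disease, so 4. Under the literal rule at a = 1 there are 200 pooled, so 20, or 100 per disease, so 10. SAP 7.2 lists 1 disease indicator + 19 comorbidities + 9 other variables = 29 candidates.

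**The case against.** The best defence is that the SAP meant what the protocol says. It calls the variable secondary loss of response in the maintenance phase and always sets it against maintained primary response, and its objectives match the protocol's. SAP 6.3 equates the reference period with the maintenance phase, and Protocol 6.1 can end that period at lack of response, so a primary non-responder might never reach a late assessment. SAP 4.2 plans a flowchart of patients in each part of the analysis, so it expects denominators to differ. Primary non-response and loss of response are also recorded as separate reasons for stopping.

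This makes a transcription slip plausible, but none of it excludes anyone. Lack of response is only one of three ways the reference period can end, the index is also collected at the study visit, and SAP 7.1 does not confine the late value to the reference period. A flowchart reports denominators without defining them.

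Two further points stand. First, the numbers rest on assumptions and include the case of no mixing. The choice of p0 matters little: at p0 = 0.30 the 2.15 becomes 2.20. Second, restricting to responders conditions on a post-baseline outcome that comorbidity may itself affect, which can introduce selection. That follows from the protocol's definition and should be acknowledged when the model is interpreted.

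**Conclusion.** The concern holds and must be fixed. The rule as written for a primary dependent variable contradicts Protocol 6.4.5 and the SAP's own comparison groups, and its physician fallback contradicts the preceding paragraph on timing. These conclusions come from the text alone and need no assumption.

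How far the results would be distorted is not determined. With 30% primary non-response and the 50% read as total non-response, contamination runs from none to 60% of events. The apparent odds ratio for a comorbidity with no effect on true loss then runs from 0.59 to 2.15, so even the direction of the error cannot be predicted. The deciding unknown is how many primary non-responders have a late value, and which value it is.

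**What to change.** In SAP 7.1, restrict loss of response and its denominator to patients classed as primary responders at 10 weeks, by index or, where the indexes are missing, by the physician's short-term judgement. In the loss-of-response fallback, change short term to long term. Name primary responders as the analysis set for Tables 14.3.1.3, 14.3.1.4 and 14.3.2.2.

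Two details make the flag programmable. Protocol 6.4.4 lists no week-10 index, so state which source sets responder status. Also state how a loss between week 10 and 6 months is counted, since the protocol's definition covers the whole follow-up.

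The work is SAP wording and one derived flag. The price is a smaller second model: about 280 patients and 80 events pooled under the assumptions above. Under the limit already in Protocol 7.4, that supports about 8 variables (about 4 per disease, against the planned maximum of 10). The protocol's definition carries this limit in any case; the literal rule would only hide it.
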